 - If necessary, a staff member will meet the participant to assist with troubleshooting. This meeting may be delayed until morning if the problem occurs overnight —in this case, the participant will use their own pump or use injectable insulin until a meeting is possible. A member of the study staff (within their scope of practice and under the supervision of the site principal investigator) may advise them on how to manage their diabetes in the interim. If necessary, the iLet device may be replaced. This may require shipping a new device to the participant. For participants in the telehealth arm, a new device will either be sent via express delivery or driven to the participant if feasible. Participants will be instructed to revert to usual care until they get the iLet.
- If there is a complete failure of the iLet operation and it is anticipated that restarting it will take more than an hour, or there is physical disconnection from the iLet that lasts longer than one hour, participants may revert to usual care using their own insulin pump or with insulin injections until the iLet can be brought back online with the help of study staff. In addition, frequent BG checks (every 2 hours and before meals) will be advised for any participant not receiving CGM data in this circumstance. Every effort should be made to correct the problem as soon as possible, which should almost always be within 24 hours
- Participants will be instructed to call the study team immediately, at any time of day or night, under any of the following circumstances:
 - They have questions or concerns
 - They want assistance troubleshooting the device
 - They have unexplained glucose over 300 mg/dL for greater than 90 minutes
 - They have ketones greater than 2.5 mmol/L (Large)
 - They have ketones greater than 0.6 mmol/L for more than 90 minutes
- If the sensor fails, it should be replaced. If the sensor is offline, participants will be instructed to self-check blood glucose at least every two hours and before meals.
 - If the sensor is offline for more than 4 hours, the sensor alerts as failed and should be replaced.

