- Participants will not tamper with or alter the iLet device in any way.
- The iLet is water resistant but participants will be instructed to remove it for showering and swimming and to keep it dry during exercise.
- Participants will be trained to take appropriate precautions when they are disconnected from the iLet, including frequent BG checks using the study Contour Next One glucometer if they are not monitoring CGM glucose by another method (e.g. their phone) and to have carbohydrate readily available. They are urged to limit the amount of time they are disconnected from the iLet to ensure optimal glucose control.
- If a participant develops an illness during the study, they can seek medical care as usual. If the participant is unable to eat for a period exceeding one day, they must notify study staff so that the medical staff can assess the safety of continuing to use the iLet. Use of the iLet may be temporarily discontinued if study staff believe this is warranted.
- If a participant discontinues use of the iLet either due to investigator judgment that it is not safe for the participant to continue to use the iLet or the participant's choice, the participant will return to their pre-study insulin delivery and glucose monitoring method and will be instructed to contact their usual diabetes care provider in case any questions or concerns arise about their usual diabetes care following cessation of study activities.

5.7.3 *Alarm Settings and Response to Hypoglycemia and Hyperglycemia*

All alarm settings will be the same during both BP arms. The blinded CGM will not have any alarms. Participants using their personal CGM as part of their usual care will be instructed to follow the alarm settings prescribed by their diabetes care provider.

- Alarms will sound and a visual alert will appear on the screen of iLet when the CGM glucose is \leq 55 mg/dl. There is an optional additional hypoglycemia alarm at 75 mg/dl. Study staff will recommend participants use this alarm as well.
 - Participants will be trained to test their BG with the study glucometer in response to such

an alarm and take any necessary measures to treat hypoglycemia as described in section 5.7.2.

- An optional alarm will sound, and a visual alert will appear on the iLet if CGM glucose is > 300 mg/dl for 90 minutes. Study staff will recommend participants use this alarm.

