6.2 Primary endpoint

- Percentage of individuals with mean CGM glucose <183 mg/dL (corresponding to an estimated HbA1c of <8.0%) on days 3-14, by group.

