6.6 Sample Size Determination

No formal statistical power or sample size calculations have been done for this study. This study is primarily intended to be a feasibility trial to verify that the iLet can be managed by both primary care physicians, endocrinologists, and delivered through telehealth.

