6.7 Statistical Analyses

An intention-to-treat analysis will be performed. Descriptive statistics will be used to summarize patient characteristics and assessments. We will estimate the percentage of participants who have a mean sensor glucose <183 mg/dl in the iLet arms of all four groups (PC-IP, PC-TH, EN-IP, EN-TH), along with confidence intervals using the Clopper-Pearson method. The hypothesis is that there is no difference in the percentage of each group that meet this metric.

The primary analysis of the designated endpoints will be calculated on an intention-to-treat basis. In cases where an arm was not completed, we will use the available data from that arm in the data analysis. We will calculate percentages, means, standard deviations (and medians and interquartile ranges as appropriate), and ranges in descriptive analyses. Unless otherwise specified, continuous data will be summarized by presenting the number of non-missing observations, mean and standard deviation (SD) or median, minimum, and maximum. Categorical data will be summarized by presenting the number of patients and percentage for each category. We will use the t-test for comparisons of means for normally distributed outcomes and the Mann-Whitney U test for comparisons of medians on non-normally distributed outcomes between groups (PC-IP, PC-TH, EN-IP, EN-TH). We will use the paired t-test for comparison of means for normally distributed outcomes and the Wilcoxon Signed Rank test for comparisons of medians on non-normally distributed outcomes when comparing between iLet and usual care within groups. There will be no adjustments for multiple comparisons.

We may, in exploratory analyses, also stratify subjects for secondary analyses of the pre-specified endpoints by the following characteristics: sex, age, usual care insulin total daily dose, body mass index, baseline A1c, and use of CGM in usual care.

P-values can be displayed to aid interpretation, not for inference. Tables, figures and listings of all primary, secondary and safety endpoints will be created.

Data from periods when the bionic pancreas was not in use will be included, if available (Dexcom CGM data may not be available in some failure modes).

All questionnaire data (including quality of life data) for patients who have completed a minimum of 4 days with a device will be included. Results will be compared by Wilcoxon signed-rank test.

6.7.1 *Safety Analyses*

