9.2 Safety Monitoring

This study is considered moderate risk. An external Data and Safety Monitoring Board (DSMB) will oversee the conduct of the study and review its results on a regular basis. Additionally, they will be informed of all serious adverse events and any unanticipated adverse device events that occur during the study. The DSMB will be informed if there are any changes to the study protocol that could significantly impact the safety or scientific validity of the study. A final DSMB meeting will convene after the completion of the study. Safety and efficacy data will also be reported to the IRB and FDA in compliance with applicable regulations.

Use of the bionic pancreas system by a participant in the study will be discontinued if any of the following occur:

- A participant experiences an episode of diabetic ketoacidosis (DKA) requiring hospitalization in the iLet arm.
 - Hyperglycemic events will be classified as DKA if all of the following are present:
 - Symptoms including but not limited to polyuria, polydipsia, nausea or vomiting
 - Serum ketones > 1.5 mmol/L or large/moderate urine ketones
 - Arterial blood pH < 7.30 or venous blood pH < 7.24 or serum bicarbonate < 15
 - Treatment provided in a healthcare facility
- A participant experiences an episode of severe hypoglycemia in the iLet arm. Severe hypoglycemia is defined as requiring the assistance of another person due to altered consciousness, and requiring another person to actively administer carbohydrate, glucagon or other resuscitative

actions. This means the participant was impaired cognitively to the point that they were unable to treat themselves, were unable to verbalize their needs, was incoherent, disoriented, and/or combative, or experienced seizure or coma. If plasma glucose measurements are not available during such an event, neurological recovery attributable to the restoration of plasma glucose to normal is sufficient evidence that the event was induced by a low plasma glucose concentration.

- The investigator believes it is unsafe for the participant to continue in the study
- A participant becomes pregnant
- The participant requests that the study be stopped

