- If more than 1 participant must have their bionic pancreas use stopped for severe hypoglycemia or DKA during the bionic pancreas arm that is not due to deliberate inappropriate use of the iLet (i.e., any two participants with a single event each), study randomization will stop and a vote of the DSMB will be required to restart. All serious and unexpected events will be reported to the DSMB within 72 hours.

Study participation is voluntary, and participants may withdraw at any time. The investigator may withdraw a participant who is not complying with the protocol. For participants who withdraw, their data will be used up until the time of withdrawal. For participants using the iLet who withdraw, a study provider will help them transition to their own therapy safely.

In case of a recurring system malfunction or participant safety issue observed with multiple participants, the overall study will be suspended while the problem is diagnosed. The study may resume if the underlying problem can be corrected by a protocol or system modification that will not invalidate the results obtained prior to suspension.

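### The primary percentage scores a person who permanently stops the iLet on whatever CGM exists, so on its own it does not show whether the iLet could be managed in each setting

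*Combined protocol and SAP*

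**What the plan says.** Section 6.2 defines the primary endpoint as "Percentage of individuals with mean CGM glucose <183 mg/dL (corresponding to an estimated HbA1c of <8.0%) on days 3-14, by group". Neither that section nor the objective in section 2.1 makes remaining on the iLet a condition of success. Section 6.7 estimates the percentage in the iLet arm of each of the four groups, by intention to treat, with Clopper-Pearson intervals.

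Three rules govern a participant who leaves the iLet early:

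- Section 6.7: "In cases where an arm was not completed, we will use the available data from that arm in the data analysis".
- Section 6.7: "Data from periods when the bionic pancreas was not in use will be included, if available".
- Section 9.2: "For participants who withdraw, their data will be used up until the time of withdrawal".

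Permanent stops are foreseen. Section 9.2 states: "Use of the bionic pancreas system by a participant in the study will be discontinued if any of the following occur". Its list covers DKA requiring hospitalization, severe hypoglycemia, the investigator's view that continuing is unsafe, pregnancy and the participant's request. After a stop, section 5.7.2 says that "the participant will return to their pre-study insulin delivery and glucose monitoring method". Temporary reversion during a device failure is a different matter, on which section 5.7.2 says: "Every effort should be made to correct the problem as soon as possible, which should almost always be within 24 hours".

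Section 6.6 gives the purpose: "This study is primarily intended to be a feasibility trial to verify that the iLet can be managed" by primary care and endocrinology, and by telehealth.

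**The concern.** Permanently stopping the iLet is direct evidence on whether it could be managed for that person, yet the primary percentage can score such a person as an iLet success. Two rules that would limit this are absent for the primary endpoint. No minimum amount of day 3-14 CGM is stated, although section 6.7 sets four days on a device for questionnaires and section 6.7.4 sets 24 hours of CGM under the exploratory analyses. Nor is it stated whether someone with no day 3-14 CGM stays in the denominator. Intention to treat does not settle that, because an available-data rule yields no value when there are no data.

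At about ten people per group, one or two stops can separate a reading of 100% from one of 80-90%. The percentage alone cannot distinguish a group in which everyone stayed on the iLet from one in which some stopped.

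**Working it through.** There is no planned figure to reproduce: section 6.6 reports no power or sample size calculation, and no success threshold is set for the group percentages. The check is a trace of the rules, followed by exact intervals.

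**1. What happens to a permanent stop after day 3.**

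- If CGM continues, usual-care days are averaged into the iLet-arm mean (section 6.7).
- If CGM ends with the stop, the mean rests on the iLet days from day 3 onward, however few. This can arise because section 5.7.2 returns the person to pre-study monitoring and nothing requires the study CGM to continue.
- If the stop leaves no day 3-14 CGM at all, the outcome is undefined.

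No rule codes any of these as non-response.

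**2. How much usual care the average can absorb.** Days 3-14 are 12 days. Suppose the iLet days average 155 mg/dl (the lispro/aspart iLet mean in the adult Bridging study, section 12.1.8), with full CGM and equally weighted days. With *a* iLet days in the window, the participant still counts if the usual-care mean is below (183 × 12 − 155 × *a*) / (12 − *a*).

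- Stop at end of day 4 (*a* = 2): (2196 − 310) / 10 = 188.6 mg/dl.
- Stop at end of day 7 (*a* = 5): (2196 − 775) / 7 = 203.0 mg/dl.

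The documents give no usual-care glucose for the primary care population, so I attach no probability to a stop being scored below 183.

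**3. Effect on a group of ten.** Assume all other members are below 183 and a 95% level (the plan does not state one). For x = n, the Clopper-Pearson lower limit is 0.025^(1/n); for x < n, the limits are the usual beta quantiles.

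| Stops | Stop scored below 183 | Stop unscorable and dropped | Stop counted as non-response |
|---|---|---|---|
| 1 | 10/10 (69.2-100) | 9/9 (66.4-100) | 9/10 = 90% (55.5-99.7) |
| 2 | 10/10 (69.2-100) | 8/8 (63.1-100) | 8/10 = 80% (44.4-97.5) |

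A stop scored at or above 183 would give the last column under the plan's own rules as well.

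**4. How often.** The number of stops is an assumption. Table 2 shows 34 of 36 starters completing the Bridging study, but section 12.1.8 describes 12 MDI and 22 pump users enrolled, which is 34. Reasons for non-completion are not given, and one of the three arms was usual care. Taking 2/36 = 5.6% (95% CI 0.7-18.7) anyway, the chance of at least one stop in ten is 1 − (34/36)^10 = 43.5%, and 7% to 87% across that interval. That range is too wide to support a forecast.

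**The case against.** The strongest reply is that the plan states intention to treat and deliberately includes off-device data. Section 2.1 calls 183 mg/dl a clinically meaningful threshold and describes the outcome as categorical. The study is descriptive, with p-values not for inference. All of this stands, and it is why the primary analysis should be kept.

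A reader might infer that a stop for severe hypoglycemia or DKA could pass unseen as a success. The documents do not support that. Both events are safety endpoints (section 6.4). The DSMB is informed of all serious adverse events. If more than one participant must stop for these events, other than through deliberate misuse, randomization halts until a DSMB vote (section 9.2).

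A reader might also infer that stops cannot be connected to primary outcomes. That is too strong. Section 6.7 promises listings of all primary endpoints, sections 6.7.2 and 6.7.3 promise individual listings, section 6.7.2 adds discontinuations with reasons, and section 6.5 adds time disconnected. With about ten per group, a reader could match them. Counts are reported with percentages, so 9/9 would be distinguishable from 10/10. What is missing is a planned by-group summary that makes the connection: the disposition summary is specified for all screened patients, with no stated split by group.

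Finally, counting every stop as failure can mislead in the other direction. A stop for pregnancy says nothing about whether primary care or telehealth can manage the iLet, and CGM loss is not the same as stopping. Both objections stand and shape the fix.

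**Conclusion.** The point holds as a limit on what the primary percentage can show. Under the available-data, off-device and withdrawal rules, a permanent stop can count as an iLet success on very little day 3-14 data. The percentage is valid as a treatment-policy summary but does not by itself answer the question in section 6.6. The harm is a potentially misleading descriptive headline, not a hidden safety event or a wrong test; the contrasted intervals overlap heavily and no decision rule in the plan would change. The shift is 10 percentage points per stop in a group of ten, if that stop would otherwise be scored below 183 or dropped and all other members are below 183. How many stops will occur is unknown.

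**What to change.** In section 6.7:

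- Keep the primary analysis. State in advance the minimum day 3-14 CGM it requires and how a participant with none is counted.
- Beside it, report by group, with Clopper-Pearson intervals, a supplementary responder percentage in which permanently stopping the iLet before the end of the arm is non-response. The denominator is everyone who starts the iLet arm. Temporary device-fault reversions under section 5.7.2 are not stops.
- Show stops by reason, and add a sensitivity version in which stops unrelated to iLet management, such as pregnancy, are not failures. Classify the reasons before the glucose results are seen.
- Show insufficient CGM as its own category, not merged with stops.
- Break the section 6.7.2 disposition table down by group and by whether the iLet arm was started, so that people randomized to usual care first who leave before the iLet arm are visible.

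The cost is wording in section 6.7 and a by-group table from data already collected; the primary endpoint does not change. The downside is that the supplementary percentage may be lower than the primary one.

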2.1 Primary objective

To assess the feasibility of deploying the iLet bionic pancreas system in the insulin-only configuration to

pump-naïve MDI users with type 1 diabetes, in the setting of being recruited from community-based primary care practices and being trained and managed by primary care providers (PC group), and in pump- and CGM-experienced (sensor-augmented pump or hybrid closed-loop) users with type 1 diabetes recruited from, trained, and managed by an academic endocrinology practice (EN group). In both practice settings, the exclusive use of telehealth (TH) visits will be assessed, as will use of in-person (IP) visits.

We will enroll 40 adult volunteers (18-85 years old) with type 1 diabetes, 20 who are insulin pump naïve MDI users enrolled from community primary care practices by University of Colorado Family Medicine (PC group) and 20 who are technology-savvy sensor-augmented pump or hybrid closed-loop users enrolled by the Massachusetts General Hospital Diabetes Clinical Research Center (EN group). Ten of the participants at each center will be trained and managed throughout the trial using in-person visits (PC-IP and EN-IP groups) and the other ten from each center will be trained and managed throughout the trial exclusively via telehealth visits (PC-TH and EN-TH groups). The 40 participants will be evenly divided into these four groups, but not by randomization. Participants will be assigned to either the in-person or telehealth arm based on the participant's preference, the participant's location, and the discretion of the investigator. Subjects in all four groups will each participate, in random order, in one 14-day study arm under their own usual care (UC arm) and one 14-day study arm under the insulin-only configuration of the iLet bionic pancreas (iLet arm).

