2.2 Secondary objectives

1. To obtain preliminary data on the quality of glycemic control among the PC and EN groups, with separate analyses in the IP and TH sub-groups, and in the UC and iLet arms within those groups, which will be used to power a larger study with a glycemic control metric as the primary outcome. Our hypotheses are that glycemic control, with key outcomes being group mean CGM glucose, the group mean time with CGM glucose less than 54 mg/dl, and the group mean time with CGM glucose in the 70–180 mg/dl range, will be similar in the PC-IP group and the EN-IP group, and in the PC-TH group and the EN-TH group in the iLet arm. Additionally, we hypothesize that glycemic control will be similar in the PC-TH group and the PC-IP group, and in the EN-TH group and the EN-IP group in the iLet arm. Further, we hypothesize that there will be a larger difference in glycemic control metrics between the UC arms versus the iLet arm in the PC group than there will be in the EN group.
2. To assess the impact of the insulin-only configuration of the iLet bionic pancreas system on psychosocial outcomes (including quality of life, fear of hypoglycemia, and diabetes distress) among study participants. Secondary analyses will be conducted between the telehealth and in-

person arm, the EN and PC groups, and the iLet and UC arms.

3 Participant Selection

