cross-over, home-use trial that compared the insulin-only iLet using lispro or aspart to the insulin-only iLet using Fiasp to usual care (UC) for 7 days each. The study enrolled 12 subjects who used MDI therapy and 22 subjects who used insulin pump for their UC. Participants at MGH ($n = 17$) used the Senseonics Eversense CGM while those at Stanford ($n = 17$) used the G5 Dexcom CGM as the input CGM to the iLet. This is the only automated insulin delivery study to test (1) two CGM devices, (2) an ultra-rapid insulin analog, and (3) a cohort including MDI and insulin pump users. Since only body weight is required to initialize the iLet, and no information is required about either insulin therapy regimen, the iLet is the only device that undergo this test without a run-in period to first determine a baseline pump therapy regimen. The iLet is ideally suited for use in underserved or insulin-pump-naïve populations, as well as in populations where endocrinologists and diabetologists are not available or are in short supply. The iLet performed equally well on MDI and insulin pump therapy subjects. Results are summarized in Figure 7.

[figure not shown]

Figure 6. Distribution of mean glucose and hypoglycemia in the Insulin-Only Bionic Pancreas Bridging Study. Mean CGM glucose level for each subject is shown over Days 3–7 under usual care, on the insulin-only iLet in using lispro or aspart, and on the insulin-only iLet using Fiasp. The mean CGM glucose and % CGM values <60 mg/dl were respectively 163 ± 26 mg/dl and 1.3% under usual care, 155 ± 13 mg/dl and 1.2% with the iLet using lispro or aspart, and 154 ± 11 mg/dl and 1.3% with the iLet using Fiasp. Red lines and circles correspond to MDI subjects and blue lines and circles correspond to insulin-pump therapy users.

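### The secondary hypotheses of similar iLet-arm glucose control are analysed only with tests of difference in cells of 10, with no interval planned for any between-group difference

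*Combined protocol and SAP*

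**What the plan says.** Section 2.2 (repeated in the Protocol Summary) names three key glycemic outcomes: mean CGM glucose, time below 54 mg/dl and time in 70-180 mg/dl. It predicts that these "will be similar in the PC-IP group and the EN-IP group, and in the PC-TH group and the EN-TH group in the iLet arm". It adds that "we hypothesize that glycemic control will be similar in the PC-TH group and the PC-IP group", and says the same of EN-TH and EN-IP. That makes four pairwise similarity hypotheses on three outcomes.

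The cells are small. Section 2.1: "Ten of the participants at each center will be trained and managed throughout the trial using in-person visits", with the other ten at each center in telehealth. Section 6.6 reports no power calculation and calls the study primarily a feasibility trial.

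For comparisons between the four groups, section 6.7 says: "We will use the t-test for comparisons of means for normally distributed outcomes and the Mann-Whitney U test for comparisons of medians". The percentage below 183 mg/dl in each group is to be reported "along with confidence intervals using the Clopper-Pearson method"; no other interval is mentioned. Group means, SDs, medians and ranges are planned as descriptive summaries. The section also says: "P-values can be displayed to aid interpretation, not for inference". No difference is named as small enough to count as similar.

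**The concern.** The hypothesis and the analysis point in opposite directions. A t-test or Mann-Whitney test asks whether there is evidence against equality. Failing to find it in 10 versus 10 is not evidence of similarity, because imprecision alone makes that result likely. The quantity that bears on similarity is the estimated difference with an interval showing which differences the data still allow, and section 6.7 does not plan it for these outcomes.

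Section 2.2 says these data will be used to power a larger study, whose design would need the size and uncertainty of the between-group differences. Without them, readers have only a p-value to set against the stated hypotheses. A modest deficit in a primary-care or telehealth cell could then be read as no difference.

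**Working it through.** The plan gives no power or precision figure for these comparisons, so there is none to reproduce. The check asks how often the planned test would fail to flag a real deficit in mean glucose, and how wide the interval would be.

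**Inputs**
- n = 10 per cell (section 2.1).
- SD of participant mean glucose on the insulin-only iLet: 13 mg/dl. The adult bridging study (Appendix A, 12.1.8) reports "155 ± 13 mg/dl and 1.2% with the iLet using lispro or aspart". The range used is 11 (bridging study with Fiasp; Monitoring study without monitoring) to 15 (Set Point study at 110 and 120 mg/dl). This is an assumption for the present cells.
- Deficit: 8 mg/dl, the bridging-study benefit (usual care 163, iLet 155). Larger insulin-only benefits come from the Monitoring study (Table 1): 164 - 151 = 13 and 165 - 148 = 17.
- Two-sided alpha 0.05, assumed, since the plan states none.

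**Formulas.** Standard error SE = SD × sqrt(2/10). Noncentrality = deficit / SE. Power comes from the noncentral t distribution with 18 degrees of freedom and critical value 2.101. The 95% half-width is 2.101 × SE.

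**Deficit of 8 mg/dl**

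| SD | SE | Noncentrality | Power | Non-significant | 95% half-width |
|---|---|---|---|---|---|
| 11 | 4.92 | 1.63 | 34% | 66% | 10.3 mg/dl |
| 13 | 5.81 | 1.38 | 26% | 74% | 12.2 mg/dl |
| 15 | 6.71 | 1.19 | 20% | 80% | 14.1 mg/dl |

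At each SD the half-width exceeds 8 mg/dl.

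**Larger deficits, iLet SD kept in both cells**
- 13 mg/dl, SD 13: noncentrality 13/5.81 = 2.24, power 56%, non-significant 44%.
- 17 mg/dl, SD 11: noncentrality 17/4.92 = 3.46, power 90%, non-significant 10%.

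**Sensitivity to the SD of the failing cell.** A cell that lost the benefit might also regain the wider usual-care spread. Simulating unequal SDs (pooled t, Welch t and Mann-Whitney) gives power of 13-14% for 8 mg/dl (SD 13 v 26), 21-24% for 13 mg/dl (SD 13 v 29) and 35-39% for 17 mg/dl (SD 11 v 29). All three deficits would then be missed more often than not. The miss rate therefore depends on both the deficit and the spread assumed.

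**Other outcomes.** The documents give no SDs for time below 54 or time in 70-180 mg/dl, so the same calculation cannot be made for them.

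**Would an equivalence margin work here?** With truly equal cells and SD 13, the 90% half-width is about 1.734 × 5.81 = 10.1 mg/dl. By simulation the 90% interval falls within ±8 mg/dl about 1% of the time and within ±10 mg/dl about 9%. For 80% power at ±8 mg/dl, the normal approximation gives 2 × [13 × (1.645 + 1.282) / 8]², or about 46 per cell.

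**The case against.** The strongest reply is that the plan does not commit the error. It declares p-values non-inferential, and no sentence says that a non-significant test will be reported as similarity. A reader might infer that such reporting is planned; the documents do not say so. The study is an unpowered feasibility trial and its secondary data are preliminary. The planned means, SDs and individual listings would let anyone compute a difference and its interval. All of this stands and limits the harm. It does not supply the missing piece: the plan states similarity hypotheses, and the only comparative output it names is a difference test.

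A reader might also infer that a group which lost the whole iLet benefit would usually look similar on all three outcomes. The documents do not support that. Only mean glucose can be calculated, and the bridging study shows almost no difference in time below 60 mg/dl (1.2% v 1.3%). Even for mean glucose, the word usually depends on taking the 8 mg/dl benefit or on giving the failing cell the usual-care SD. Some insulin-only studies (Stanford, Day-camp) showed no mean-glucose benefit to lose. Section 2.2 expects a larger gain in the primary-care group but gives no figure.

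Finally, a strict margin rule would add little here. Truly equal cells would almost never meet it, and the groups are not randomised and also differ in site and pump experience. That objection stands, so a margin is not part of the change proposed.

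**Conclusion.** The point holds as a mismatch between hypothesis and analysis: four similarity hypotheses, tests of difference only, cells of 10, and no interval for any between-group difference. For mean glucose, under SD 13 mg/dl (11-15), normality and two-sided 0.05, a true 8 mg/dl deficit would go unflagged about 74% of the time (66-80%), and a 95% interval would extend about 12 mg/dl either side of the estimate (10-14). The miss rate drops for larger deficits if the narrow iLet SD persists. The mismatch itself does not depend on these figures, which show only how little a non-significant result would say. The point is worth correcting, but the non-inferential status of the p-values and the feasibility purpose keep it from being grave.

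**What to change.** In section 6.7, for the four hypothesised iLet-arm comparisons (PC-IP v EN-IP, PC-TH v EN-TH, PC-TH v PC-IP, EN-TH v EN-IP), make the estimated between-group difference with its 95% confidence interval the main result, in place of the difference test. Use the difference in means for mean CGM glucose and time in 70-180 mg/dl, and a Hodges-Lehmann or bootstrap interval for time below 54 mg/dl. Suggested wording: *A non-significant p-value will not be taken as evidence of similarity; the confidence interval shows which differences remain compatible with the data.*

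A formal equivalence margin is optional and better left to the larger study, which can be sized for it.

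The cost is a few sentences and twelve intervals (four comparisons × three outcomes) on data already collected. The downside is that the intervals will be wide, so the trial will often be unable to claim similarity.
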